4. PLANNED ANALYSES

4.1. INTERIM ANALYSIS

There are no plans for interim analyses whose intent would be to stop the study early or to adapt the study design or planned number of patients. There will be two planned analysis time points during the study. The first analysis will occur after all subjects complete the phone call or office visit 1 [30 days (+ 14 days) post-surgery]. All data collected through 30-day (+14 days) follow-up will be analyzed.

The second analysis will occur after all subjects complete the phone call or office visit 2 [6-month (+/-30 days) post-surgery] and the data collected at this follow-up is available. The second analysis will be performed on the data from the 6-month follow-up assessing any occurrences of SAEs requiring surgical intervention and assessed as possibly related, probably related, or related to the randomized study treatment.

5. ANALYSIS SETS

Agreement and authorization of subjects included/ excluded from each analysis set will be conducted prior to the unblinding of the study.

5.1. ALL SUBJECTS RANDOMIZED SET [RND]

The all subjects randomized (RND) set will contain all subjects who were randomized to study device.

For analyses and displays based on RND, subjects will be classified according to randomized treatment.

5.2. Intent-to-Treat analysis set (ITT)

Intent-to-Treat (ITT) analysis set consists of all enrolled subjects for whom TBS was identified. Subjects who do not complete the procedure after TBS identification will be included in the ITT. Subjects were randomized to treatments.

5.3. PER PROTOCOL ANALYSIS SET (PP)

Per-Protocol (PP) analysis set (set of evaluable subjects) consists of all ITT subjects who have no major protocol deviations affecting the primary effectiveness endpoint and have data available for this endpoint.. Subjects will be classified according to randomized treatment.

Major protocol deviations will be determined prior to database lock.

5.4. SAFETY ANALYSIS SET

Safety analysis set consists of all subjects who received study product. Subjects will be classified according to actual treatment received and at least post-baseline follow up.

6. GENERAL CONSIDERATIONS

6.1. REFERENCE START DATE AND STUDY DAY

Study Day will be calculated from the reference start date and will be used to show start/stop day of

assessments and events.

Reference start date is defined as the surgical procedure day (Day 1 is the day of surgical procedure) and will appear in every listing where an assessment date or event date appears.

• If the date of the event is on or after the reference date, then:

Study Day = (date of event - reference date) + 1.

• If the date of the event is prior to the reference date, then:

Study Day = (date of event – reference date).

In the situation where the event date is partial or missing, Study Day, and any corresponding durations will appear partial or missing in the listings.

6.2. BASELINE

Unless otherwise specified, baseline is defined as the last non-missing measurement taken prior to reference start date (including unscheduled assessments). In the case where the last non-missing measurement and the reference start date coincide, that measurement will be considered prebaseline, but Adverse Events (AEs) and medications commencing on the reference start date will be considered post-baseline.

6.3. WINDOWING CONVENTIONS

Study procedures and evaluations performed at each visit are included in section 11 of the protocol.

6.4. STATISTICAL TESTS

The default significant level will be 5%; confidence intervals will be 95% and all tests will be two-sided, unless otherwise specified in the description of the analyses.

6.5. COMMON CALCULATIONS

The statistical analysis of the data obtained from this study will be performed using SAS® version 9.4 or higher.

Unless otherwise specified, descriptive statistics for continuous variables will be presented using the number of non-missing observations, mean, standard deviation, median, minimum and maximum. In general, the same number of decimal places as in the raw data will be presented when reporting minimum and maximum, one more decimal place than in the raw data will be presented when reporting mean and median, and two more decimal places than in the raw data will be presented when reporting standard deviations. If the raw data have three or more decimals, three decimals will be presented for mean, median, minimum and maximum, and standard deviation.

For categorical endpoints, descriptive statistics will be presented using the frequency counts and percentage of subjects in the various categories of the variable. All percentages will be presented with one decimal, except percentages less than one, which should be presented with 2 decimals or more, as appropriate.

7. STATISTICAL CONSIDERATIONS

For the primary or secondary effectiveness endpoints, the analyses based on the ITT set will consider missing data as failures. Missing data for safety endpoints will not be imputed.

8. OUTPUT PRESENTATIONS

The template provided jointly with SAP describes the output presentation of this study. The format and content of summary tables, graphs and lists are provided by Kuntuo Biostatistics.

9. DISPOSITION AND WITHDRAWALS

All subjects who provide informed consent will be accounted for in this study.

Subject disposition and withdrawals, and protocol deviations, including inclusion and exclusion criteria, will be presented for all subjects.

The assignment of subjects to analysis populations, completion of study/ premature termination of study and protocol deviations/other reasons for exclusion from analysis sets will be summarized in frequency tables. Detailed information will be provided in listings.

10. DEMOGRAPHIC AND OTHER BASELINE CHARACTERISTICS

Demographic and baseline characteristics will be summarized descriptively as described in section 6.5. Demographic characteristics, such as age, gender, and race, will be summarized for the ITT set. In addition, the descriptive statistics for other baseline characteristics will include, but will not limited to medical/surgical history, concomitant medications, and various laboratory data, and will be presented for the Safety analysis set.

Detailed information will be provided in listings.

11. PRIOR MEDICAL /SURGICAL HISTORY

A pre-existing condition is one that is present at the start of the study and is to be reported as part of the subject's medical history. It must be reported as a new Adverse Event if the intensity, frequency, or the character of the condition worsens during the study treatment.

Relevant information in this section will be presented to the Safety set and described separately by treatment group.

12. CONCOMITANT MEDICATIONS

Indication and start-stop dates of concomitant medications administered from 24 hours prior to surgery up to the 30-day follow-up phone call or office visit will be documented on the Concomitant Medication eCRF. This will include medications used chronically (even if temporarily halted for surgery) and those medications administered as a prophylactic before, during and after surgery.

Anesthetics used for study surgery and over the counter (OTC) drugs will not be recorded as concomitant medication. Concomitant medications used to treat Adverse Events (even if the concomitant medication is an OTC drug or nutritional supplement) must also be documented.

Concomitant medications will be presented for the Safety set and will be summarized separately by treatment group.

13. EFFECTIVENESS OUTCOMES

13.1. PRIMARY EFFECTIVENESS ENDPOINT

The primary effectiveness endpoint is defined as the proportion of subjects achieving hemostatic success at 5 minutes following the application of SURGICEL Powder or SURGICEL Original with no

re-bleeding requiring additional treatment at the TBS any time prior to initiation of final fascial closure.

13.1.1. ANALYSIS OF PRIMARY EFFECTIVENESS ENDPOINT

The primary effectiveness endpoint will be analyzed using the ITT and the PP sets. The primary analysis will be based on the PP set. The ITT analysis will be considered supportive.

The statistical hypothesis for testing the treatment group difference for primary effectiveness endpoint is presented as follows:

 H_0 : $P_T - P_C \le -0.1$ tested against the alternative hypothesis

 $H_1: P_T - P_C > -0.1.$

 P_C is the proportion of successes in Control group, and P_T is the proportion of successes in Test group.

Two hundred and ten (210) evaluable subjects (105 per study arm) will achieve 80% power to detect a non-inferiority margin difference in group proportions of 0.1 using a Farrington-Manning score test with a one-sided significance level of 0.025. The proportion of successes in the Control group is assumed to be 0.8. The proportion of successes in Test group is assumed to be 0.7 under the null hypothesis of inferiority. The power was computed for the case when the actual proportion of successes in the Test group is 0.85.

For the primary effectiveness endpoint, a one-sided 97.5% confidence interval for P_T - P_C will be constructed using the Farrington-Manning (FM) score method. If the lower limit of the one-sided 97.5% confidence interval is greater than -0.1, then it will be concluded that the SURGICEL Powder is non-inferior to SURGICEL Original. If the non-inferiority of SURGICEL Powder is established, the superiority of SUGICEL Powder to SURGICEL Original will then be evaluated; if the lower limit of one-sided 97.5% confidence interval is greater than 0, then it will be concluded that the SURGICEL Powder is superior to SURGICEL Original. In addition, two-sided 95% confidence intervals for the proportion of successes in each treatment group separately will be constructed using the Clopper-Pearson method.

Within each TBS bleeding severity level (Mild, Moderate), the primary effectiveness endpoint will be summarized descriptively by treatment group and overall, using frequency counts and associated percentages.

In In addition, a sensitivity (secondary) analysis for the primary effectiveness endpoint will be performed to evaluate the comparability across the 2 strata by using a logistic regression model, with success/failure for primary endpoint as dependent variable and with stratification factor (mild/moderate), treatment group and interaction between stratification factor and treatment group as independent variables included in the model.

An example of SAS code is provided below:

proc logistic data=primaryend;

class treatment success;

model success= treatment strata treatment*strata / expb;

run;

It is not anticipated that there will be data missing for the primary or secondary effectiveness endpoints, but, if these is, the analyses based on the ITT set will consider missing data as failures for these endpoints.

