13. STATISTICAL CONSIDERATIONS

13.1. Analysis Sets

The following three analysis sets are defined:

Confidential Page 62 of 86

- Intent-to-Treat (ITT) analysis set consists of all subjects for whom TBS was identified. Subjects who do not complete the procedure after TBS identification will be included in the ITT.
- Per-Protocol (PP) analysis set (set of evaluable subjects) consists of all ITT subjects who have no major protocol deviations and have data available for primary effectiveness endpoint.
- Safety analysis set consists of all subjects who received study product.

The primary effectiveness endpoint will be analyzed using the ITT and the PP sets. However, the primary analysis will be based on the PP set. The ITT analysis will be considered supportive.

All secondary effectiveness endpoints will be analyzed using the ITT set, while safety endpoints will be analyzed using the Safety set.

It is not anticipated that there will be data missing for the primary or secondary effectiveness endpoints, but, if there is, the analyses based on the ITT set will consider missing data as failures for these endpoints. Missing data for safety endpoints will not be imputed.

Major protocol deviations are deviations that have an impact on the primary effectiveness endpoint. These will be determined prior to database lock.

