For the primary effectiveness endpoint, a one-sided 97.5% confidence interval for P_T - P_C will be constructed using the Farrington-Manning (FM) score method. If the lower limit of the one-sided 97.5% confidence interval is greater than -0.1, then it will be concluded that the SURGICEL Powder is non-inferior to SURGICEL Original. If the non-inferiority of SURGICEL Powder is established, the superiority of SUGICEL Powder to SURGICEL Original will then be evaluated; if the lower limit of one-sided 97.5% confidence interval is greater than 0, then it will be concluded that the SURGICEL Powder is superior to SURGICEL Original. In addition, two-sided 95% confidence intervals for the proportion of successes in each treatment group separately will be constructed using the Clopper-Pearson method.

The primary endpoint will be analyzed using the Intent-to-Treat (ITT) and Per-Protocol (PP) sets. The PP analysis will be considered the primary analysis, while the ITT analysis will be considered supportive. The analysis sets for this study are defined in Section 13.1.

The following **secondary efficacy endpoints** will be summarized descriptively by treatment group and overall, for the ITT analysis set:

Confidential Page 64 of 86

- Proportion of subjects achieving hemostatic success at 3 minutes following the application of SURGICEL Powder or SURGICEL Original with no re-bleeding requiring additional treatment at the TBS any time prior to initiation of final fascial closure;
- Proportion of subjects achieving hemostatic success at 10 minutes following the
 application of SURGICEL Powder or SURGICEL Original with no re-bleeding
 requiring additional treatment at the TBS any time prior to initiation of final
 fascial closure.

For the binary (success/failure) secondary effectiveness endpoints (3 and 10 minutes hemostasis endpoints), within-treatment group two-sided 95% confidence intervals will be reported for the proportion of successes using the Clopper-Pearson method. A two-sided 95% confidence interval for the difference in proportion of successes between treatment groups (Test minus Control) will also be calculated for each binary secondary effectiveness endpoint using the FM score method; however, no testing for non-inferiority will be carried out.

In addition, the following **safety endpoints** will be summarized descriptively by treatment group and overall, for the Safety analysis set:

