13.6. Criterion of Acceptability/Unacceptability of Clinical Trial Result

For the primary effectiveness endpoint, a one-sided 97.5% confidence interval for P_T - P_C will be constructed using the Farrington-Manning (FM) score method. If the lower limit of the one-sided 97.5% confidence interval is greater than -0.1, then it will be concluded that the SURGICEL Powder is non-inferior to SURGICEL Original. If the non-inferiority of SURGICEL Powder is established, the superiority of SUGICEL Powder to SURGICEL Original will then be evaluated; if the lower limit of one-sided 97.5% confidence interval is greater than 0, then it will be concluded that the SURGICEL Powder is superior to SURGICEL Original.

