2. STUDY OBJECTIVES

The objectives of this 2-arm registration study are to evaluate the safety and to demonstrate non-inferiority of hemostatic effectiveness of SURGICEL Powder compared with SURGICEL Original in controlling mild or moderate parenchymal or soft tissue intraoperative bleeding during general, gynecological, and cardiothoracic surgery in Chinese adult (≥18 years old) subjects.

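### Superiority can be declared on the per-protocol set alone, because the plan does not require the ITT analysis to show it (minor)

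*SAP*

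**What the plan says.** The stated objective is "to demonstrate non-inferiority of hemostatic effectiveness of SURGICEL Powder compared with SURGICEL Original" (SAP 2; Protocol 3.1 agrees). Superiority is a follow-on step. Protocol 13.6, the acceptability criterion, says "If the non-inferiority of SURGICEL Powder is established, the superiority of SUGICEL Powder to SURGICEL Original will then be evaluated", and SAP 13.1.1 gives the rule: "if the lower limit of one-sided 97.5% confidence interval is greater than 0, then it will be concluded that the SURGICEL Powder is superior". The same rule stands in the protocol synopsis and in Protocol 13.2.

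The analysis sets are assigned once for the whole primary-endpoint analysis. SAP 13.1.1 says "The primary analysis will be based on the PP set. The ITT analysis will be considered supportive"; Protocol 13.2 says "The PP analysis will be considered the primary analysis, while the ITT analysis will be considered supportive". None of the four statements of the superiority rule gives that step a set of its own or makes it depend on ITT.

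PP is the ITT set minus subjects with major deviations judged to affect the primary endpoint and minus those without endpoint data (SAP 5.3). For ITT, "the analyses based on the ITT set will consider missing data as failures for these endpoints" (Protocol 13.1). On timing, SAP 5 says "Agreement and authorization of subjects included/ excluded from each analysis set will be conducted prior to the unblinding of the study" and SAP 5.3 says "Major protocol deviations will be determined prior to database lock". SAP 9 has exclusions and their reasons tabulated and listed.

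**The concern.** Leading with PP is a defensible choice for non-inferiority and is not questioned here. A superiority claim is different: it should rest on the comparison that randomization protects. PP removes subjects after treatment, by judging whether a deviation touched the endpoint. Only the subject is blinded (Protocol 11.3.6), and the investigator assesses hemostasis (Protocol 10.1.12). If exclusions fell more on failures in one arm, the PP difference would shift with no real effect behind it.

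What is at stake is a formal superiority statement, written into the acceptability criterion of a registration study, that the supportive analysis need not confirm. The planned safeguards would make a disagreement between the sets visible, but the plan would still let the PP result stand.

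**Working it through.** **Inputs.** From Protocol 13.2 and 13.3.1 and SAP 13.1.1: one-sided alpha 0.025, margin 0.10, success rates 0.85 (Powder) and 0.80 (Original), 105 evaluable and 117 randomized per arm, Farrington-Manning (FM) score method. Exclusion patterns are not in the documents; every pattern below is an assumption.

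**1. The plan's own sample size.** The restricted rates at a difference of -0.10 are 0.7597 and 0.8597.
- s0 = √(0.7597×0.2403 + 0.8597×0.1403) = 0.551
- s1 = √(0.85×0.15 + 0.80×0.20) = 0.536
- n = [(1.960×s0 + 0.842×s1)/0.15]² = 104.1, so 105 per arm; 105/0.9 = 116.7, so 117 per arm.

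Both figures reproduce. Power at 105 per arm is 80.3% by this approximation.

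**2. Can the two sets disagree?** At a difference of 0 the FM statistic is the pooled score statistic, z = (pT − pC)/√[p(1−p)(1/nT + 1/nC)], and superiority needs z > 1.960. Take an ITT result of 104/117 against 94/117, which is close to the threshold.
- ITT: p = 198/234, difference 0.0855, z = 1.81, FM lower limit -0.0072. Not superior.
- One Powder failure excluded, 104/116 against 94/117: p = 198/233, difference 0.0931, z = 1.99, lower limit +0.0014. Superior.
- One failure excluded per arm, 104/116 against 94/116: lower limit -0.0050. Not superior.
- One Powder success excluded, 103/116 against 94/117: lower limit -0.0086. Not superior.

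So disagreement is possible, and one exclusion can decide it.

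**3. How often, when there is no true difference (0.80 in both arms)?** Exact enumeration at 117 per arm gives false superiority of 2.5% on ITT. Excluding one Powder failure creates a PP-only claim in 1.0% of trials.

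False superiority on PP with more exclusions (simulation, 1,000,000 trials per row):

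| Assumed exclusions | PP false superiority |
|---|---|
| None | 2.5% |
| 10% at random, both arms | 2.5% |
| 10% of failures, both arms | 2.5% |
| 10% of Powder failures only (117×0.20×0.10 ≈ 2.3 subjects) | about 5% |
| 10% of Original failures only | 1.1% |

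**4. Power for superiority at 0.85 against 0.80** (exact enumeration): 17.1% on ITT with 117 per arm and complete data; 15.6% on PP with 105 per arm. If outcomes are missing equally in both arms and count as failures, ITT power is 15.7% at 2% missing, 14.0% at 5% and 11.9% at 10%.

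**The case against.** The strongest reply is that PP-primary is a stated choice. SAP 13.1.1 assigns the sets at its opening, and the superiority rule follows on the same endpoint and interval. That stands: a reader might infer that the deciding set is left undefined, but the natural reading is that PP decides. The point is that ITT agreement is not required, not that a definition is missing.

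A reader might also infer that the type I error is inflated. The documents do not support that. Doubling it takes exclusions confined to Powder failures, nothing in either document indicates such a pattern, and the reverse pattern makes PP conservative. SAP 14.7 says the PP wording was aligned with how the deviation assessment had been performed. That does not show that arm or outcome influenced the assessment.

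Discordance rates at 0.85 against 0.80 look more striking: 4.3% of trials for one excluded Powder failure. But Powder truly is better there, so a PP-only claim would be correct. The 80/80 figure of 1.0% is the relevant one, and the example in step 2 was chosen at the decision boundary.

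ITT is not flawless either. SAP 5.2 defines it by identification of a target bleeding site and does not clearly say that subjects are classified by randomized arm. Counting missing as failure could favour Powder if Original outcomes were missing more often. Both points stand and shape the fix. The plan expects no missing outcomes.

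The safeguards are real. Because the investigator knows the arm, agreement before unblinding is partial protection, but nothing shows that it failed.

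**Conclusion.** The point holds as a minor one. As written, the plan permits a superiority conclusion on PP that ITT does not support. Whether this would matter depends on which subjects are excluded, and the documents do not give that. With exclusions unrelated to outcome, or symmetric between arms, the 2.5% error rate is kept; under the assumed one-sided patterns it ranges from 1.1% to about 5%. The error rate of a PP-based superiority claim is therefore not guaranteed, which is a weaker statement than saying it is inflated. Priority is low because the objective is non-inferiority, superiority is conditional on it, and the power for superiority is only about 16 to 17% at the planned rates. The non-inferiority conclusion is not affected.

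**What to change.** In SAP 13.1.1, state: *Superiority is concluded only if the lower limit exceeds 0 in the ITT set, with each subject in the randomized arm and a missing outcome counted as failure; PP is supportive for this step.* Protocol 13.9 allows the change in an amended SAP, with its impact reported in the clinical study report. For consistency, carry the same sentence into the protocol synopsis, 13.2 and 13.6 at the next amendment. Leave the PP-primary non-inferiority analysis as it is.

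The cost is small. The ITT analysis with missing counted as failure is already planned, so no new data, alpha or sample size is needed. At the planned sizes superiority power is slightly higher on ITT than on PP, but it can fall below PP if outcomes are missing (step 4). Unequal missingness between arms could bias ITT, so the number of missing outcomes per arm should be shown beside the ITT result.

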11.4.2. Definition of Target Bleeding Site

The TBS will be defined as the first accessible bleeding site identified during dissection, related to the primary operative procedure requiring an adjunctive hemostat.

Once the TBS is identified and conventional techniques were considered impractical or ineffective, the surgeon will apply the randomized treatment at the TBS to cover the entire bleeding area. The bleeding severity will describe the intensity of the bleeding that is present at the time the surgeon determines that an adjunctive hemostatic product is required. At each investigational site enrollment will be stratified into two groups, according to TBS bleeding severity (mild or moderate bleeding).

As a frame of reference, only target bleeding sites with mild or moderate bleeding as defined by the following scale of bleeding intensity will be included:

Mild Bleeding: A TBS with a small area of capillary, arteriole, or venule oozing.

Moderate Bleeding:

1. A TBS with a larger area of capillary, arteriole, or venule oozing that presents a significant challenge because of the larger area involved, increasing the volume of blood loss.

or

2. A TBS with bleeding that is more pronounced than oozing, which could also

Confidential Page 56 of 86

come from a small artery or vein, but is not massive, pulsatile, and flowing.

Severe Bleeding (excluded by this protocol):

Bleeding (arterial, venous, or mixed) that is rapidly flowing, pulsatile, or spurting, which in the surgeon's judgment requires rapid control to prevent hemodynamic consequences (e.g. hypovolemia, tachycardia, or hypotension) and could involve major volume loss which if not treated rapidly, could be life threatening. SURGICEL Powder and SURGICEL Original should not be used in place of sutures or other forms of mechanical ligation for the treatment of major arterial or venous bleeding or major defects in arteries and veins.

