3. STUDY DESIGN

This is a single blind, prospective, randomized, multicenter, multispecialty, controlled clinical study comparing SURGICEL Powder with SURGICEL Original (control arm) as an adjunct to achieve hemostasis in the control of capillary, venous, and small arterial hemorrhage when ligation or other conventional methods of control are impractical or ineffective during surgery (open, laparoscopic, or thoracoscopic) in Chinese adult subjects.

The number of evaluable subjects required for this trial is 210 subjects (105 per treatment arm). In order to account for a potential 10% drop-out rate, at least 234 evaluable subjects (117 per treatment arm) with an appropriate mild or moderate Target Bleeding Site (TBS) will be randomized in a 1:1 allocation ratio to either SURGICEL Powder or SURGICEL Original (control). Randomization will be stratified by investigational site and TBS bleeding severity (mild or moderate bleeding).

Study subjects will be enrolled in approximately 12 study sites. The number of subjects enrolled in any site should not exceed 46 subjects (20% of the total sample size).

After application of either SURGICEL Powder or SURGICEL Original, the TBS will be assessed for hemostasis (no detectable bleeding) at 3, 5, and 10 minutes from application and prior to initiation of final fascial closure on open surgery or port site closure in laparoscopic or thoracoscopic surgical procedures.

All enrolled subjects will be followed post-operatively through discharge, and via phone call or office visit at 30 days (+14 days) post-surgery. In addition, all enrolled subjects will receive a 6-month (+/-30 days) follow-up phone call or office visit to assess the occurrence of any SAE requiring surgical intervention and assessed as possibly related, probably related, or related to the study treatment.

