13.2.1. ANALYSIS OF SECONDARY EFFICACY VARIABLES

The secondary effectiveness endpoints will be summarized descriptively by treatment group and overall, using frequency counts and associated percentages, for the ITT analysis set.

For the binary (success/failure) secondary effectiveness endpoints (3 and 10 minutes hemostasis endpoints), within-treatment group two-sided 95% confidence intervals will be reported for the proportion of successes using the Clopper-Pearson method. A two-sided 95% confidence interval for the difference in proportion of successes between treatment groups (Test minus Control) will also be calculated for each binary secondary effectiveness endpoint using the FM score method; however, no testing for non-inferiority will be carried out.

In addition, within each TBS bleeding severity level (Mild, Moderate), the binary secondary effectiveness endpoints will be summarized descriptively by treatment group and overall, using frequency counts and associated percentages.TO consult Farrington-Manning (FM) 1 method to calculate the percentage difference and the confidence interval through the following procedure: proc freq data=raw1;

tables trt*ae1or0 / riskdiff(cl=FM) nopercent nocol; run:

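### Randomization is stratified by bleeding severity, but no planned analysis gives a severity-adjusted risk difference to set against the -0.1 margin; the crude interval is valid but may be wider than it needs to be

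*SAP*

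**What the plan says.** **Randomization.** SAP 3 states: "Randomization will be stratified by investigational site and TBS bleeding severity (mild or moderate bleeding)." Protocol 11.3.6 and 13.2 agree, and 11.3.6 has the surgeon classify severity before the envelope is opened. Protocol 11.4.2 describes one form of moderate bleeding as oozing over a larger area that "presents a significant challenge because of the larger area involved, increasing the volume of blood loss".

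**Deciding analysis.** In Protocol 13.2 the one-sided 97.5% interval for P_T - P_C "will be constructed using the Farrington-Manning (FM) score method". Protocol 13.6 gives the rule: "If the lower limit of the one-sided 97.5% confidence interval is greater than -0.1, then it will be concluded" that the powder is non-inferior. SAP 13.1.1 repeats both: the interval there "will be constructed using the Farrington-Manning (FM) score method. If the lower limit of the one-sided 97.5% confidence interval is greater than -0.1", with the same conclusion drawn. None of these places mentions strata or weights. The only Farrington-Manning (FM) code in the SAP, given for the secondary endpoints in 13.2.1, is a plain two-way table: "tables trt*ae1or0 / riskdiff(cl=FM) nopercent nocol".

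**Where severity does appear for the primary endpoint.** SAP 13.1.1 tabulates success by arm within mild and moderate bleeding. It also plans a sensitivity analysis "to evaluate the comparability across the 2 strata by using a logistic regression model", with treatment, severity and their interaction as terms.

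**The concern.** A factor used to stratify randomization is normally carried into the analysis. If severity predicts hemostasis, the crude variance includes between-severity variation that the design has already balanced. The crude interval is then conservative and wider than necessary.

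The logistic model does not fill the gap. It works on the odds scale, its interaction term leaves no single treatment effect, and no conversion to a risk difference is planned. So nothing planned can be compared with -0.1 after allowing for severity.

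There is also a robustness issue. The primary set is PP, and exclusions can undo the severity balance that randomization created. The crude difference would carry that imbalance uncorrected.

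**Working it through.** **1. The plan's own figure.** Inputs from SAP 13.1.1: control 0.80, test 0.85, margin -0.1, one-sided 0.025. The FM restricted estimates at -0.1 are 0.7597 and 0.8597.

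- Null SD = sqrt(0.7597×0.2403 + 0.8597×0.1403) = 0.5506.
- Alternative SD = sqrt(0.85×0.15 + 0.80×0.20) = sqrt(0.2875) = 0.5362.
- Power at 105 per arm = Φ[(0.15×√105 - 1.96×0.5506)/0.5362] = Φ(0.854) = 80.3%. At 104 per arm it is 79.96%.
- Exact enumeration at 105 per arm gives power 81.3% and one-sided error 2.54%.
- Dropout: 210/0.9 = 233.3, so 234.

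The stated size is right for the unstratified test.

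**2. Assumptions for the comparison.** The documents give no mild/moderate pair of success rates. The only severity-specific control rate (Protocol 7) is 80% in mild bleeding at 4 minutes. Assumed here: half the subjects mild, control averaging 80%, test +5 points in each stratum, 105 per arm.

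**3. Half-width.** This is a Wald-type guide: 1.96×sqrt((V_T + V_C)/105). Crude V = 0.2875, giving 0.1026. Stratified V is the average within-stratum variance. For a 20-point gap (control 0.90/0.70, test 0.95/0.75), V = (0.0475+0.1875)/2 + (0.09+0.21)/2 = 0.2675, giving 0.0989.

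**4. Power and error.** These are simulated for the score test itself: Z = Σw_k(d_k+0.1)/sqrt(Σw_k²V_k), with w_k = n1k·n2k/(n1k+n2k) and V_k the FM restricted variance in stratum k. The set-up is 12 sites × 2 severities, blocks of 4 (assumed) and 210 evaluable subjects.

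| Gap (points) | Stratified half-width (crude 0.1026) | Narrower | Power, crude / stratified | Error, crude / stratified | Conclusions differ |
|---|---|---|---|---|---|
| 0 | 0.1026 | 0% | 81.1 / 81.2% | 2.5 / 2.5% | 0.4% |
| 10 | 0.1017 | 0.9% | 81.3 / 81.6% | 2.4 / 2.5% | 1.0% |
| 20 | 0.0989 | 3.5% | 82.3 / 83.3% | 2.3 / 2.5% | 2.0% |
| 30 | 0.0942 | 8.2% | 82.9 / 84.7% | 1.9 / 2.5% | 3.0% |

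The 30-point row is a boundary case, because test success in mild bleeding is 100%. With 70% mild, where 30 points is not a boundary, the narrowing is 0%, 0.7%, 3.0% and 6.8%, the power gain is 0.1, 0.3, 1.2 and 2.5 points, and stratified error is 2.5% to 2.6%. If the arms are forced into exact balance within severity, power at the 20-point gap is 82.2 against 83.0%, and differing conclusions are rarer (0.1%, 0.4%, 1.1% and 1.6%).

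**5. Imbalance in the PP set (illustrative).** Take 117 per arm, half mild (58.5), and 12 excluded per arm. If Test loses 9 mild and 3 moderate and Control the reverse, the mild shares are 49.5/105 = 47.1% and 55.5/105 = 52.9%. The crude difference shifts by (0.471 - 0.529)×gap = -0.057×gap, which is 0.6, 1.1 or 1.7 points for gaps of 10, 20 or 30. The sign depends on which arm loses more mild cases.

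**The case against.** The strongest reply is that nothing here is wrong. The sample size, the test and the interval agree with one another, and the trial reaches its 80% power without stratification. The gain is small: 0.3 points of power for a 10-point gap and 1.0 for 20. Stratified randomization already passes part of the benefit to the crude test, whose power rises from 81.1% to 82.9% as the gap grows. A pure Wald comparison suggests up to about 6 points of power, but it misses this and should not be used. All of this stands.

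Nor do the documents show that severity predicts 5-minute hemostasis. The Protocol 11.4.2 wording concerns area and blood loss, and the 80% in mild bleeding equals the planned overall rate. This stands too, so the size is conditional on assumed gaps.

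The effect may also differ by severity. With a 20-point gap and test +0 in mild, +10 in moderate, narrowing falls to 2.2% (V = 0.125 + 0.15 = 0.275; sqrt(0.275/0.2875) = 0.978), and power is 81.7 against 82.6%. With an overall difference of -0.1 made up of -20 in mild and 0 in moderate, simulated stratified error was between 2.5% and 2.75%. That is at most a trivial cost.

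The by-severity counts would let a reader compute a stratified difference. But an analysis chosen after the results are known does not carry the weight of a prespecified one. The PP example is deliberately uneven, and severity weighting would not remove bias from outcome-related exclusions. These points lower the priority of the concern without answering it.

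**Conclusion.** The concern holds. Severity is a randomization factor, and no planned analysis gives a severity-adjusted risk difference to compare with -0.1. The crude FM interval is valid and the sample size is correct, so this is a missed efficiency and a robustness gap rather than an error.

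Nothing is lost if severity is not prognostic. For assumed gaps of 10 to 20 points the loss is about 1% to 3.5% of interval width and 0.3 to 1.2 points of power, across the two severity mixes. It is larger only if the gap approaches 30 points. These figures rest on an assumed severity mix, assumed gaps, a constant +5-point effect and assumed blocks of 4. The change is worth making because it is nearly free, but it is not critical to the trial's conclusion.

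**What to change.** Prespecify a severity-stratified score interval for the risk difference: two strata, Mantel-Haenszel weights, FM restricted variance within each stratum, and the same -0.1 and 0 thresholds.

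- **If no one has seen outcomes by arm:** make it primary and keep the unstratified FM interval as the sensitivity analysis. This means editing the synopsis, Protocol 13.2, 13.4 and 13.6, SAP 13.1.1 and the change list in SAP 14.7. Ethics and regulatory approval may be needed if the amendment counts as major under Protocol 20.
- **If outcomes by arm have been seen:** leave the unstratified interval as primary and add the stratified one as a labelled sensitivity analysis on both PP and ITT. SAP 14.7 speaks of the protocol-deviation assessment as already done, so the timing should be confirmed and recorded. This route costs one SAP paragraph and a few lines of code, and Protocol 13.9 allows it through an amended SAP.

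Do not stratify the primary interval by site as well: 12 × 2 = 24 cells leaves 210/24 = 8.75 evaluable subjects per cell. A site-adjusted sensitivity analysis is optional.

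A separate minor correction: the example logistic code in SAP 13.1.1 has "class treatment success". The `CLASS` statement should list the severity variable rather than the response, and the model should name success as the event.
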